Data source provenance/curation: In brief, all databases provide EHR-derived oncology-specific patient-level information which are either derived directly (e.g., through structured data fields and dropdown menu selections) from EHR and/or undergo semi-automated abstraction processes from unstructured reports. The detailed data provenance, abstraction processes and implemented business rules to curate and prioritize certain variables may vary by database and can be found in legacy publications by the data partners.

Table 3. Metadata about data sources and software.

	EDB1	EDB3	EDB4
Data Source(s):	EHR-derived	EHR-derived	EHR-derived
Study Period:	Patient identification period: 01/01/2011-04/30/2024 with follow-up information through data cut-off date on 04/30/2024	Follow-up information through June 2023 (there is no specific time period restrictions for patient eligibility)	Patient identification period: 10/01/2018-09/30/2023 with follow-up information through data cut-off date on 09/30/2023.
Eligible Cohort Entry Period:	Anytime at start of study drug initiation	Anytime at start of study drug initiation	Anytime at start of study drug initiation
Data Version (or date of last update):	Delivery: Jul 11, 2024	Delivery: Jun 16, 2023	Delivery: Oct 24, 2023 Updated (demographics): Feb 29, 2024

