6.6.5. Context and rationale for outcome(s) of interest

The primary outcome for the database study was defined to emulate the primary outcome for the trial, time from index to death due to any reason (OS).

Operational definitions:

- **EDB1:** Time in [days, months and years] from index date to death due to any reason. The date of death is de-identified to month-level granularity or (rarely) to year-level granularity and the date of death is therefore imputed to the 15th of a month or mid-year/July 2 of the year of death, respectively. In If there is no indication that a patient died during the study period, the patient is censored. The censoring date is defined as the last visit or treatment encounter or data cut-off date, whichever occurred earlier. The OS endpoint is operationalized using a parameterized R function *edb1_get_os()* and more details can be found in the attached pdf documentation.
- **EDB3:** Time in [days, months and years] from index date to death due to any reason. The date of death is de-identified to month-level granularity and the day of death is therefore imputed to the 15th of a month. Patients without evidence of death are censored at the earlier of the last recorded activity date or the data cut-off date. Activity dates are defined as documented in Table 4. Death dates are compiled from Electronic Medical Records (EMR), manual curation, and third-party death data, linked via de-identified tokens generated from hashed personally identifiable information (PII). Sources of death dates are prioritized as follows: (1) manual curation, (2) EMR, and (3) third-party sources. For privacy reasons, the final reported death date is shifted to the nearest Sunday within four days of the actual date. Manually curated death dates follow a prioritization hierarchy of source documentation: death certificate first, followed by scanned obituaries or death announcements, and lastly exact dates reported by providers without other supporting documentation. The OS endpoint calculation uses a parameterized R function (*edb3_get_os()*), with detailed documentation provided in the attached PDF.

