Sensitivity #4	Censoring date is changed to 3 months before data cut-off date	For all databases, information on mortality comes from different data sources which are updated asynchronously. To account for the potential lag of updated mortality information (ghost-time bias ³⁷), the censoring for patients without mortality event in the whole patient identification period will be moved to last sign of patients being alive/visit or 3 months before data cut-off date, whichever occurred earlier. ³⁸	Approach implements a more conservative censoring rule	Approach addresses ghost-time bias by censoring patients without a recorded death event earlier
Sensitivity #5	Delta imputation models for MNAR (tipping point analysis)	Primary multiple imputation analysis assumes MAR which	Estimates impact of deviations from MAR assumption on final	Delta parameters must be assumed and results are complex to interpret in

		may not hold for every covariate	treatment effect estimates for key covariates	multivariate missingness settings; just most important covariates or those with highest suspicion of being MNAR will be evaluated
Sensitivity #6	Re-weighting of strong risk factors and/or treatment effect modifiers distribution to match that of PALOMA-2	In the presence of effect modification, treatment effect estimates may be different if the distribution of strong risk factors/effect modifiers is different in the emulated cohort versus the trial cohort	Re-weighting adjusts for differences in distributions of key risk factors and/or treatment effect modifiers (see subgroup analysis in Table 7)	Re-weighting risk factors/potential effect modifiers to match the PALOMA-2 trial and simultaneously balancing them across treatment groups may be challenging due to differences in measurement
Sensitivity #7	Including patients who have had at least 1 visit 90 days prior to treatment initiation	EHR are often lacking data continuity, and this analysis uses the requirement of 1 visit as a proxy for continuous observation periods	Considers aspect of data continuity	There may be patients who are put on treatment immediately in which case they are falsely excluded

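### Sensitivity #4 cuts follow-up at 3 months before cut-off only for patients with no recorded death, so its censoring depends on the outcome; a common cut for all patients should replace it

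*Combined protocol and SAP*

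**What the plan says.** In the primary analysis, patients with no recorded death are censored at their last activity (section 6.6.5). For EDB1, "The censoring date is defined as the last visit or treatment encounter or data cut-off date, whichever occurred earlier". For EDB3, "Patients without evidence of death are censored at the earlier of the last recorded activity date or the data cut-off date".

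Table 8 gives the reason for Sensitivity #4: "information on mortality comes from different data sources which are updated asynchronously". Three cells of that row describe the change:

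- What is varied: "Censoring date is changed to 3 months before data cut-off date".
- Detailed rule: "the censoring for patients without mortality event in the whole patient identification period will be moved to last sign of patients being alive/visit", followed by "or 3 months before data cut-off date, whichever occurred earlier".
- Limitation: "Approach addresses ghost-time bias by censoring patients without a recorded death event earlier".

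The second and third cells make the earlier censoring conditional on having no recorded death. The first cell carries no such condition. No cell says what happens to a death recorded in the last 3 months. In EDB1 the identification period in Table 3 runs to the cut-off itself, so a patient who dies in that window does have a death within the whole period, and her follow-up is not moved.

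**The concern.** Under the detailed rule, whether a patient's follow-up stops at cut-off minus 3 months depends on whether she is later recorded as dead. In the last 3 calendar months the only person-time left belongs to patients who die there, and their deaths count. That is informative censoring by construction. It pushes the estimated hazard up and the Kaplan-Meier median down, by more as more late deaths are captured.

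The row calls the rule more conservative and does not list this dependence as a limitation. Sensitivity #4 is the only Table 8 analysis aimed at the timing of death reporting, and section 6.1.1 names mortality ascertainment as a limitation of the data. If #4 differs from the primary result in absolute survival, the reader cannot tell how much is reporting lag and how much is the rule.

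**Working it through.** **The plan's own figure.** Sensitivity #4 has no figure of its own. The nearest is the power in section 10.3, from Schoenfeld's formula with 50% exposed, HR 0.92 and alpha 0.05 (two-sided reproduces it): power = Φ(|ln 0.92|·√(events/4) − 1.96).

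- EDB1: 0.0834 × √(1021/4) = 1.332; Φ(−0.628) = 0.265. The plan says 0.27.
- EDB3: 0.0834 × √(331/4) = 0.758; Φ(−1.201) = 0.115. The plan says 0.11.

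**Inputs from the documents.** Entry 2015-2022, or 96 months (Table 7). EDB1 "with follow-up information through data cut-off date on 04/30/2024", which is 112 months after January 2015. EDB3 has follow-up through June 2023, taken as 101.5 months (Table 3). Letrozole-arm median in the trial, 51.2 months (section 4).

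**Assumptions not in the documents.** Exponential survival; uniform entry unless stated otherwise; a fraction f of deaths in the last 3 months captured, varied from 0 to 1; in the simulation, last activity 0-1 month before death or cut-off.

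**Closed form for the rule as written.** Let λ = ln 2/51.2 = 0.01354 per month and c = cut-off minus 3.

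- Share alive at c: S = [e^(−λ(c−96)) − e^(−λc)]/(96λ)
- Share dead by c: D0 = 1 − S
- Share dying in the window: Dw = S(1 − e^(−3λ)) = 0.0398·S
- Mean time in the window for those who die there: 1.49 months
- Estimated/true hazard = (D0 + f·Dw)/(D0 + f·λ·1.49·Dw)

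EDB1 (c = 109): S = 0.4694, D0 = 0.5306, Dw = 0.0187. At f = 1 the ratio is 0.5493/0.5310 = 1.034.

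EDB3 (c = 98.5): S = 0.5410, D0 = 0.4590, Dw = 0.0215. At f = 1 the ratio is 0.4805/0.4594 = 1.046.

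At f = 0 both ratios are 1.

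**Simulation** (600,000 patients per arm, same entry dates in both arms). Estimated/true control hazard:

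| Capture | EDB1 primary | EDB1 #4 as written | EDB1 common cut | EDB3 primary | EDB3 #4 as written | EDB3 common cut |
|---|---|---|---|---|---|---|
| 0% | 0.974 | 1.003 | 1.003 | 0.961 | 0.998 | 0.998 |
| 25% | 0.982 | 1.011 | 1.002 | 0.976 | 1.014 | 1.002 |
| 50% | 0.990 | 1.019 | 1.002 | 0.984 | 1.022 | 0.999 |
| 75% | 0.999 | 1.028 | 1.001 | 0.993 | 1.031 | 0.997 |
| 100% | 1.006 | 1.035 | 1.001 | 1.003 | 1.041 | 0.995 |

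At full capture, separate runs and the closed form put EDB3 between 1.041 and 1.047. At 25% capture #4 is closer to the truth than the primary rule (EDB1 error 1.1% against 1.8%). At 50% it is further away (1.9% against 1.0%). The common cut stays within about 0.5% throughout.

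**Median.** At full capture the control median under #4 is 49.7 months in EDB1 (51.2 − 49.7 = 1.5) and 49.5 in EDB3 (51.2 − 49.5 = 1.7). Under the common cut it stays at 51.0-51.4 at every capture fraction.

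**Hazard ratio.** With equal entry dates and a true HR of 0.96, #4 gives 0.957-0.965, the same as the primary rule. Table 5 encodes index year only as before 2020 or 2020 onward, so matched arms can still differ in entry date within a level. With the two levels balanced, entry skewed in opposite directions within them and a true HR of 1.00, #4 gives:

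- 5-month gap in mean entry: 1.000-1.011 over 25-100% capture.
- 7.4-month gap, full capture: 1.010 (EDB1) and 1.016 (EDB3).
- 17-month gap: 1.009-1.015 at 25-50% capture; 1.023 (EDB1) and 1.035 (EDB3) at full capture.

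**The case against.** The strongest defence is that the rule does what it was written for. Late reporting means that some late deaths are missing. If none of the deaths in the last 3 months is captured, #4 is essentially exact while the primary rule understates the hazard by 2.6% (EDB1) or 3.9% (EDB3). At 25% capture it is still the better of the two. EDB3 was delivered on 16 June 2023, in the month its follow-up ends, so low capture is plausible there. This stands, and a reader who infers that #4 adds bias instead of correcting lag goes too far. It does not rescue the rule. EDB1 was delivered about 10 weeks after cut-off, so substantial capture is plausible there, and the common cut is approximately unbiased at every capture fraction.

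The first cell may also mean a common cut, and the documentation of the OS functions is not available here. That stands as well: retention of late deaths is inferred from the conditional wording, which is clear but not explicit. It is a reason to reconcile the cells.

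Three stronger readings are tempting and are not supported:

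- *The HR from #4 is biased or uninterpretable.* With equal entry dates it does not move. A skew across the whole entry period (mean gap 32 months), with every late death captured, moves a true 0.96 to 1.002 (EDB1) and 1.023 (EDB3), but that sets aside the adjustment for index year. The documents as available do not give entry dates in the matched sets.
- *A fall of 1.5-1.7 months rivals the trial's arm difference of 2.7 months (53.9 − 51.2).* With similar entry dates the fall is common to both arms, so it is not comparable with a between-arm contrast.
- *#4 should also probe bias from stopping survivors at their last visit, which would be differential if letrozole-alone patients are seen less often.* The documents give no visit frequency by arm, and EDB3's last activity draws on many record types (Table 4). Following patients beyond their last sign of life would also restore the ghost time that #4 is meant to remove.

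**Conclusion.** The point holds for the rule as written: earlier censoring is conditional on having no recorded death, so the analysis is free of this bias only if no late death is captured. Over 0-100% capture the hazard is inflated by 0-3.5% in EDB1 and 0 to about 4.7% in EDB3, and the median falls by up to about 1.5-1.7 months. These sizes rest on exponential survival with median 51.2 months, uniform entry over 2015-2022 and an unknown capture fraction. The upper ends apply only when every late death is captured, in which case there is no lag to correct. An HR shift of roughly 1-3% needs both residual calendar-time imbalance and high capture.

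Severity is minor to moderate. This is one of twelve sensitivity analyses, the primary estimate does not depend on it, and the harm falls mainly on absolute survival.

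**What to change.** Rewrite Sensitivity #4 as one rule for all patients: follow-up ends at the earliest of death, last activity, or cut-off minus 3 months; a patient whose death is recorded after that last date is censored there and the death is not an event. Align the first cell and the limitation cell with this rule.

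The cost is a few lines of text and the loss of late deaths from this analysis. If all of them are captured, that is Dw/(D0 + Dw):

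- EDB1: 0.0187/0.5493 = 3.4%, so 1021 events become about 986 and power goes from 0.27 to about 0.26.
- EDB3: 0.0215/0.4805 = 4.5%, so 331 events become about 316 and power stays at about 0.11.

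No change to the primary analysis is needed.

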6.6. Setting

6.6.1. Context and rationale for definition of time 0 (and other primary time anchors) for entry to the study population

Time 0 in this database study is defined as the date a patient initiated palbociclib plus letrozole (exposure) or letrozole alone (comparator) as part of their 1L systemic antineoplastic treatment for advanced/metastatic adenocarcinoma of the breast. This aims to emulate the date of randomization and cohort entry in the RCT (the time from randomization to first dose is not reported in the [clinicaltrials.gov study report](https://clinicaltrials.gov/study/NCT02420417) or the trial articles).

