6.6.4. Context and rationale for exposure(s) of interest

The exposure and comparator were defined to emulate the agents compared for the trial, i.e., initiation of palbociclib plus letrozole versus letrozole alone in a 1L metastatic setting.

- **EDB1:** Exposure is derived using a manually curated line of therapy (LOT) table provided by the data partner that programmatically categorizes treatment regimens into a coherent line of treatment, based on a proprietary business rule with an exposure assessment window. That is, each patient is represented with one row per curated line of therapy with corresponding information on line number, regimens as well start and end dates. Based on this table, patients are identified who received palbociclib-plus-letrozole or letrozole-alone treatment regimen by their generic names (string match) in 1L, using the exposure assessment window; follow-up begins after the end of the exposure assessment window. The LOT implicitly only considers regimens that were given as part of a metastatic disease setting. Importantly, the LOT table applies a proprietary business rule to determine line of therapy, which includes an exposure assessment window relative to advanced cancer diagnosis. More details and annotated code to identify initiators can be found in the 'Derive cohort EDB1' Quarto report (access within MGB network only).
- **EDB3:** Exposure is derived using a manually curated line of therapy (LOT) table provided by the data partner that programmatically categorizes treatment regimens into a coherent line of therapy, based on a proprietary business rule with an exposure assessment window. That is, each patient is represented with one row per curated line of therapy AND drug name with corresponding information online number, regimens as well start and end dates. Based on this table, patients are identified who received only palbociclib and letrozole within the first line of therapy, and letrozole alone within the first line of therapy by their generic names (string match), using the exposure assessment window; follow-up begins after the end of the exposure assessment window. The LOT implicitly only considers regimens that were given as part of a metastatic disease setting. More details and annotated code to identify initiators can be found in the 'Derive cohort EDB3' Quarto report' (access within MGB network only).
- **EDB4:** For the EDB4 database, the following logic is applied.

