Socio-economic status	dem_ses	edbx_get_demographics()	Socioeconomic status (SES) index based on residence area of patient. Not available in EDB3 and EDB4.	Nominal (from '1 - Lowest SES' through '5 - Highest SES')	[-inf;0]
Smoking	c_smoking_history	edbx_get_demographics()	History of current or former (= TRUE) or never (= FALSE) smoking on or anytime before index date; if there are multiple records per patient, any evidence of former/current smoking is prioritized. IN EDB1, "smoking history" is not available for breast cancer.	Binary logical (TRUE, FALSE)	[-inf;0]
ECOG	c_ecog	edbx_get_ecog()	ECOG performance status measured closest to index date within assessment window. In	Nominal (0, 1, 2, 3, 4); modelled as ordinal numeric in ROPRO ¹⁰ ; due to I/E	[-90;0]

Characteristic	Harmonized analysis variable name	R function to derive covariate (see pdf in appendix)	Details ¹	Variable encoding	Assessment window
			case of ties, the lower ECOG value is selected	criteria ECOG is modelled as a binary (0, 1) covariate	
Stage	c_stage_initial_dx	edbx_get_diagnosis_solid()	AJCC summary group stage at initial diagnosis	Ordinal numeric (from 0 to IV with sub-categories, e.g., IA1) ¹⁰	[-inf;0] at initial diagnosis of primary cancer
De novo metastatic status	c_de_novo_mets_dx	edbx_get_diagnosis_solid()	Evidence of presence of one or multiple metastases at/before initial diagnosis	Binary logical (TRUE, FALSE)	[-inf;0] at initial diagnosis of primary cancer
Number of metastatic sites	c_number_met_sites	edbx_get_diagnosis_solid()/edbx_get_number_met_sites_solid()	Number of metastatic sites for a given patient before/on index date	Integer	[-inf;X]; Proprietary business-rule-based covariate assessment window
Time between initial diagnosis to index date	c_time_dx_to_index	edbx_get_diagnosis_solid()	Time in days between initial diagnosis to index date. Quartiles will be used because there may be “negative” times intervals due to date imprecision of the lines of therapy.	Categorical (quartiles)	[-initial dx;0]
Time between earliest evidence of a metastatic and index date	c_time_met_dx_to_index_quartiles	edbx_get_diagnosis_solid()	Time in days between earliest evidence of a metastatic diagnosis and index date. Quartiles will be used because there may be “negative” times intervals due to date imprecision of the lines of therapy.	Categorical (quartiles)	[met dx;0]

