Sensitivity #8	Using all available calendar time	This analysis explores potential confounding related to calendar time, evolving clinical practice patterns, and access to therapies.	Aims to assess the extent of confounding introduced by changes in time, treatment practices, and access to therapies.	We expect the results to be more confounded due to calendar time.
Sensitivity #9	Missingness is handled by restricting to patients with complete observations on a subset of the most important confounders (“complete cases”).	Instead of imputing data, this sensitivity analysis restricts the analysis cohort to patients with complete observations on key confounders	Data will not be imputed and missingness is assumed to be missing completely at random	The restriction to complete cases will significantly decrease sample size. To limit the attrition of patients with partially observed covariates, it won’t be possible to use all covariates used in the main analysis propensity score model, but only consider key covariates with overall low proportions of missingness (age, sex, etc.)
Sensitivity #10	Exclusion of patients with >1 year between metastasis diagnosis and index date	This sensitivity analysis varies the inclusion criteria by excluding patients whose index date (treatment start) is >1 year after their metastatic diagnosis date which is	Helps ensure that treatment reflects initial first-line treatment of metastatic disease, not late-line therapy.	Exclusion of further patients results in a smaller cohort size which may reduce statistical power.

		clinically unrealistic or implausible for a first-line treatment		
Sensitivity #11	Addition of EDB4	EDB4 is not considered in primary analyses for reasons given in section 6.1.1.	Increased sample size and potentially broader coverage of general US cancer population	See limitations listed in section 6.1.1 regarding potential immortal time and selection bias due to left truncation .
Sensitivity #12	Descriptive analysis of switching/crossover patterns in the trial and its emulation	This sensitivity analysis assesses crossover patterns comparatively in the trial and its emulation	Help to understand the potential concordance/discordance of treatment effects between the trial and its emulation	Analysis is on the description level, which may limit conclusions

7. Limitation of the methods

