Inclusion 3	Documentation of histologically or cytologically confirmed diagnosis of estrogen-receptor positive (ER+) breast cancer based on local laboratory results.	[-inf; 0]	Any ER+ or ER missing status to or on index date	Any ER+ or ER missing status to or on index date	Any ER+ or ER missing status to or on index date	If ER is missing and a patient received the exposures of interest, then ER is likely to be positive given the alignment with the indication for the exposures of interest	edbx_get_biomarker()
Inclusion 4	Previously untreated with any systemic anti-cancer therapy for their locoregionally recurrent or metastatic ER+ disease.	[MBC; -1]	No systemic anti-cancer therapy following initial record potentially indicating metastatic disease and prior to index date	No systemic anti-cancer therapy following initial record potentially indicating metastatic disease and prior to index date	No systemic anti-cancer therapy following initial record potentially indicating metastatic disease and prior to index date		
Inclusion 5	Postmenopausal women defined as women with: - Prior bilateral surgical oophorectomy, or - Medically confirmed post-menopausal status defined as spontaneous cessation of regular menses for at least 12 consecutive months or follicle-stimulating hormone (FSH) and estradiol blood levels in their respective postmenopausal ranges with no alternative pathological or physiological cause.	NA	NA	NA	NA	Although not directly captured in RWD, it is likely to be fulfilled given the alignment with the indication for the exposures of interest	
Inclusion 6	Measurable disease as defined per RECIST v.1.1 (see Appendix 7) or bone-only disease (with bone lesions confirmed by CT, MRI or bone X-ray). Tumor lesions previously irradiated or subjected to other locoregional therapy will only be deemed measurable if disease progression at the treated site after completion of therapy is clearly documented.	NA	NA	NA	NA	It is reasonable to assume that all patients in RWD had measurable disease if they received treatment	
Inclusion 7	World Health Organization Performance Status of 0 to 1	[-90; 0]	ECOG = 0 1	ECOG = 0 1	ECOG = 0 1		edbx_get_ecog()
Inclusion 7	Restriction to period 2015-2022	[0; 0]	Years 2015-2022	Years 2015-2022	Years 2015-2022		

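### Starts more than one year after metastatic diagnosis stay in the primary cohort, and the propensity score sees that gap only as quartiles with no one-year cut

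*Combined protocol and SAP*

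**What the plan says.** Section 6.6.1 sets time 0 at the start of study treatment given "as part of their 1L systemic antineoplastic treatment for advanced/metastatic adenocarcinoma of the breast". The rule that protects first-line status, Inclusion 4 of the eligibility appendix, reads "No systemic anti-cancer therapy following initial record potentially indicating metastatic disease and prior to index date". It looks for recorded therapy between the first metastatic date and the day before index, and puts no upper limit on the length of that interval. Table 2 has none either.

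The limit appears only in Table 8, Sensitivity #10: "Exclusion of patients with >1 year between metastasis diagnosis and index date". The row calls such a gap "clinically unrealistic or implausible for a first-line treatment" and gives as its strength "Helps ensure that treatment reflects initial first-line treatment of metastatic disease, not late-line therapy". Because it "This sensitivity analysis varies the inclusion criteria by excluding patients whose index date (treatment start) is >1 year after their metastatic diagnosis date", these women are in the primary cohort.

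Table 5 (section 6.6.7) defines the gap as "Time in days between earliest evidence of a metastatic diagnosis and index date", codes it in quartiles, and justifies this by negative intervals arising from imprecise line-of-therapy dates. It gives no cut-points. Section 7 does not discuss long gaps.

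**The concern.** The plan flags a group as doubtful for first-line treatment, keeps it in the primary analysis without giving a reason, and adjusts for the flagged feature in a form that cannot isolate the group.

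A woman who starts more than a year after her first metastatic record may have had treatment that the record does not show, may have slow-growing disease, or may have a wrong date. The first two affect prognosis, in directions that need not agree. If the mix differs between arms after matching, the OS comparison carries residual confounding. The matched balance display would not reveal it, because it is drawn on the covariates as coded.

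Screening for earlier therapy is not complete protection. Section 7 concedes that poor data continuity may misclassify exposure. The Table 2 footnote on prior systemic therapy omits anastrozole and fulvestrant, which section 6.6.4 lists as antineoplastics for EDB4. In EDB1 and EDB3, finding their use after metastatic diagnosis therefore rests on vendor line-of-therapy rules that are not disclosed.

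**Working it through.** **1. Can quartiles isolate the group?** Let f be the share of the cohort with a gap above 365 days (not given in the documents). If f is below 25%, all these women fall in the top quartile and make up f/0.25 of it:

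- f = 5%: 0.05/0.25 = 20%
- f = 10%: 0.10/0.25 = 40%
- f = 15%: 0.15/0.25 = 60%

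The rest of that quartile started within a year. If f exceeds 25%, the one-year point lies in a lower quartile and is still not separated.

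**2. Would the balance check notice?** Suppose every quartile holds 25% of each arm, so the quartile ASMD is 0, and assume that 3% of one arm and 8% of the other exceed 365 days. These are 12% and 32% of the top quartile. For an indicator of more than 365 days,

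ASMD = (0.08 − 0.03) / √[(0.03×0.97 + 0.08×0.92)/2] = 0.05/0.227 = 0.22.

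This is above the 0.1 benchmark that section 6.7.1 uses by analogy with propensity scores, yet the coded covariate shows no imbalance.

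**3. What could it do to the OS hazard ratio?** Assume constant hazards, balanced quartiles, a hazard ratio h for gaps above versus up to one year, and a between-arm difference d in the above-one-year share of the top quartile, centred on f/0.25. With p_T = f/0.25 + d/2 and p_C = f/0.25 − d/2,

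multiplier = [1 + 0.25·p_T·(h − 1)] / [1 + 0.25·p_C·(h − 1)].

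For f = 10%:

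| d | h = 0.6 | h = 1.67 |
|---|---|---|
| 10 points | 0.990 | 1.016 |
| 20 points | 0.979 | 1.032 |
| 30 points | 0.969 | 1.048 |

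Worked case, d = 30 points: p_T = 0.55 and p_C = 0.25. For h = 0.6, 0.945/0.975 = 0.969. For h = 1.67, 1.092/1.042 = 1.048. Over f = 5% to 15% the extremes are 0.969 and 1.050. These figures put the larger share in the palbociclib arm. Swapping the arms gives the reciprocals, about 0.95 to 1.03.

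**4. What would removing the group cost in power?** The Schoenfeld formula, power = Φ(√(events/4)·|ln 0.92| − 1.96), uses the section 10.3 inputs (two-sided alpha 0.05, equal allocation).

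- EDB1, 1021 events: 0.265 (stated 0.27).
- EDB3, 331 events: 0.115 (stated 0.11).
- Pooled, 1021 + 331 = 1352 events: 0.335.

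The stated figures reproduce. At an assumed 10% loss of events, pooled power is 0.307, and the ratio of upper to lower 95% confidence limit rises from 1.238 to 1.252. Power therefore does not decide the matter.

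**The case against.** The strongest defence is that Sensitivity #10 already runs the exclusion, with its rationale and its cost in cohort size stated. The trial criteria reproduced in Table 2 and the appendix require no earlier systemic therapy for advanced disease but set no limit on time since metastatic diagnosis. Keeping the trial's rule in the primary cohort and testing the limit as a sensitivity analysis is a sound emulation choice. Some long gaps may also be date error in women who are truly first-line, since the clock starts at the earliest evidence of metastasis and Table 5 itself warns of imprecise dates. All of this stands. A reader might infer that the 365-day exclusion must move into the primary cohort; for these reasons the documents do not support that.

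A reader might also infer that the propensity score cannot balance these women at all. That goes too far. Gap quartiles, time since initial diagnosis, de novo status, stage and number of metastatic sites are all listed covariates, so balance is partial and not assured. Nor is the gap immortal time: it precedes time 0.

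Finally, the EDB1 line-of-therapy rule, "which includes an exposure assessment window relative to advanced cancer diagnosis", might cap the gap there. That cannot be seen from the documents, and Sensitivity #10 would then have nobody to remove in EDB1.

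**Conclusion.** The point holds as a gap in adjustment and in wording. The primary cohort has no upper limit on the interval, the plan itself doubts first-line status beyond one year, and quartile balance does not ensure balance on that group.

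The size is unknown. No counts or quartile cut-points are given, and the attrition and balance figures were not available for this check. A multiplier of roughly 0.97 to 1.05 rests entirely on the assumed shares and hazard ratios, and its direction is open. It is of the same order as the distance of the trial's OS hazard ratio, 0.96, from 1, so it matters for judging concordance even though it lies within the sampling error.

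A larger distortion might be inferred from, say, 5% versus 15% affected with a mortality ratio of 2.0: (1 + 0.05)/(1 + 0.15) = 0.91. With quartiles balanced, that needs 20% versus 60% of the top quartile, and a doubling of risk that persists after adjustment for the other prognostic factors. Nothing in the documents supports so extreme a case. Nor do they show that late-line patients are actually present in the primary cohort; they show only that the plan considers it possible.

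**What to change.** - In Table 5, add a separate level for more than 365 days to the metastatic-diagnosis-to-index covariate, keeping quartiles or finer categories below it. Negative intervals remain in the lowest category, so the stated reason for categorising is respected.
- Include that level in the primary propensity-score model.
- Show its post-match ASMD across imputed datasets, and the number of women above 365 days by arm and database, before and after matching.
- Keep the exclusion as Sensitivity #10. Reconcile its wording with primary eligibility by stating why these women are retained, for example because dates are imprecise and the trial criteria set no such limit.

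The cost is one more propensity-score term and possibly slightly fewer matched pairs. The interval is already derived for Sensitivity #10, so no new data are needed, but the matching and balance output must be rerun.
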